1. Unwillingness to stop taking pain or antispasmodic medication other than the study medication (specifically opioid use [e.g., Vicodin], barbiturates, and cannabis).
2. Chronic back pain for the previous 3 months or longer, on more days than not.
3. Radicular pain in the lower extremity (i.e. pain radiating below the knee), sciatica pain down the leg, or pain below the knee (indicating a lumbar radiculopathy); radicular pain in the upper extremity, radiating into the forearm or hand (indicating a cervical radiculopathy).
4. Concomitant severe pain in a region other than the back.
5. Spinal surgery within 1 year of study entry.
6. Back pain due to major trauma (e.g., motor vehicle accident, fracture of bone) unless resolved for more than 1 year.
7. Treatment of back pain ongoing with non-pharmacological therapy (e.g. acupuncture, chiropractic adjustment, massage, Transcutaneous Electrical Nerve Stimulation [TENS], physiotherapy).
8. Female subjects who are pregnant or lactating.
9. Subjects who are taking Baclofen (Lioresal, Liofen, Gablofen, etc.) or Botox (onabotulinumtoxin A) for pain.
10. Subjects who test positive for alcohol by breathalyzer test.
11. Known history or symptoms suspicious of:
 - a. Spinal fracture within previous 3 years
 - b. Osteoporosis with fracture
 - c. Cancer except cutaneous cancers (e.g., melanoma, squamous cell carcinoma)
 - d. Constitutional symptoms such as recent unexplained chills or weight loss
 - e. Spinal infection
 - f. Intravenous drug abuse
 - g. Immunosuppression
 - h. Cauda equina syndrome
 - i. History of chronic severe scoliosis (childhood).
12. Myasthenia gravis.
13. Recent history of severe hepatic insufficiency, i.e., aspartate aminotransferase (AST)/alanine aminotransferase (ALT) above 3 times the upper limit of normal (ULN).
14. Recent history of severe renal insufficiency, i.e., serum creatinine value above 2.5 mg/dL.
15. History or presence of a severe infection, major surgery or trauma, severe metabolic, endocrine or electrolyte disturbances.
16. A major illness, requiring hospitalization during the 3 months before commencement of the screening period.
17. Inflammatory arthritis or other diseases known to cause intermittent or chronic pain.
18. Subjects who have had a recent history (less than 2 years before entering the study) of drug or alcohol abuse, or current positive urine drug screen. Alcohol abuse is defined as current consumption of more than three alcoholic beverages per day.

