9. SUBJECT DEFINITION

A sufficient number of subjects will be screened to ensure the enrollment of approximately 400 subjects. Individuals are eligible for this study if they meet all inclusion and no exclusion criteria. The criteria below will be assessed at the Screening/Baseline visit.

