9.1. Inclusion Criteria

1. Ambulatory male or female, 18 to 65 years of age.
2. Current acute back pain and/or stiffness due to acute and painful muscle spasm starting within 7 days prior to study entry and more than 8 weeks after the last episode of acute back pain.
3. Subjects must have pain of 4 or more on the subject “right now” rating of pain intensity NRS scale of 0 – 10 points at baseline.
4. Must be willing to discontinue all medication used for the treatment of pain or muscle spasm on study entry at Day 1 including but not restricted to:
 - a. Ibuprofen (Motrin)
 - b. Diclofenac (Voltaren)
 - c. Celocoxib (Celebrex)
 - d. Naproxen (Aleve)
 - e. Tolmetin (Tolectin)
 - f. Cyclobenzaprine (Flexeril)
 - g. Cyclobenzaprine (Amrix)
 - h. Metaxolone (Skelaxin)
 - i. Methocarbamol (Robaxin)
 - j. Other nonsteroidal anti-inflammatory drugs (NSAIDs; e.g., aspirin)
 - k. Carisoprodol (Soma)
 - l. Tizanidine (Zanaflex, Sirdalud)
5. Pain localized below the neck and above the inferior gluteal folds.
6. Body mass index ranging between 18 and 35 kg/m².
7. All subjects must be capable of understanding and complying with the protocol and have signed the informed consent document.
8. Female subjects must have a negative urine pregnancy test at screening, must be postmenopausal (amenorrhea for at least 2 years), surgically sterile, or practicing or agree to practice an effective method of birth control if they are sexually active before study entry, during the study and for 2 weeks after the end of the study by using an acceptable method of contraception. Acceptable methods of birth control must be used for at least 14 days prior to the use of study drug. Acceptable methods of birth control include oral, injectable, subdermal implant, vaginal or patch contraceptives, intrauterine device (IUD; copper or hormonal IUD), or double-barrier method (e.g., condom, diaphragm or cervical cap with spermicidal foam, cream, gel, or suppository).
9. Subjects must be willing and able to comply with scheduled visits, treatment plan, laboratory tests, and other study procedures.

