9.2. Exclusion Criteria

1. Unwillingness to stop taking pain or antispasmodic medication other than the study medication (specifically opioid use [e.g., Vicodin], barbiturates, and cannabis).
2. Chronic pain for the previous 3 months or longer, on more days than not.
3. Radicular pain in the lower extremity (i.e. pain radiating below the knee), sciatica pain down the leg, or pain below the knee (indicating a lumbar radiculopathy); radicular pain in the upper extremity, radiating into the forearm or hand (indicating a cervical radiculopathy).
4. Concomitant severe pain in a region other than the back.
5. Spinal surgery within 1 year of study entry.
6. Back pain due to major trauma (e.g., motor vehicle accident, fracture of bone) unless resolved for more than 1 year.
7. Treatment of back pain ongoing with non-pharmacological therapy (e.g., acupuncture, chiropractic adjustment, massage, Transcutaneous Electrical Nerve Stimulation [TENS], physiotherapy).
8. Female subjects who are pregnant or lactating.
9. Subjects who are taking Baclofen (Lioresal, Liofen, Gablofen, etc.) or Botox (onabotulinumtoxin A) for pain.
10. Subjects who test positive for alcohol by breathalyzer test.
11. Known history or symptoms suspicious of:
 - a. Spinal fracture within previous 3 years
 - b. Osteoporosis with fracture
 - c. Cancer except cutaneous cancers (e.g., melanoma, squamous cell carcinoma)
 - d. Constitutional symptoms such as recent unexplained chills or weight loss
 - e. Spinal infection
 - f. Intravenous drug abuse
 - g. Immunosuppression
 - h. Cauda equine syndrome
 - i. History of chronic severe scoliosis (childhood)
12. Myasthenia gravis.
13. Recent history of severe hepatic insufficiency, i.e., aspartate aminotransferase (AST)/alanine aminotransferase (ALT) above 3 times the upper limit of normal (ULN).
14. Recent history of severe renal insufficiency, i.e., serum creatinine value above 2.5 mg/dL.
15. History or presence of a severe infection, major surgery or trauma, severe metabolic, endocrine or electrolyte disturbances.
16. A major illness, requiring hospitalization during the 3 months before commencement of the screening period.
17. Inflammatory arthritis, or other diseases known to cause intermittent or chronic pain.

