18. Subjects who have had a recent history (less than 2 years before entering the study) of drug or alcohol abuse, or current positive urine drug screen. Alcohol abuse is defined as current consumption of more than three alcoholic beverages per day.
19. History of seizure disorder other than Infantile Febrile Seizures, family history of seizure, or history of head trauma with loss of consciousness.
20. Disability claim for back pain, or pending legal issue regarding back pain.
21. Subjects who have received treatment with an investigational product/device within 30 days prior to study entry.
22. Subjects who have a history of allergic reaction to tolperisone, eperisone, or other skeletal muscle relaxants, lidocaine, acetaminophen or NSAIDs or any components of these study medications.
23. Any other condition that, in the opinion of the Investigator, would adversely affect the subject's ability to complete the study or its measures.
24. Subjects who are unwilling to stop taking moderate to potent inhibitors of cytochrome P450 (CYP) isozymes CYP2D6 and CYP2C19, which are likely to cause drug interactions with tolperisone HCl (e.g., medications such as paroxetine and fluvoxamine).
25. Subjects who are a site staff member, relative, or friend of a site staff member or subjects in same household or who are related to each other.
26. Subjects with clinically significant cardiovascular disorders, such as ischemic heart disease, arrhythmias, poorly controlled hypertension, or history of acute myocardial infarction.
27. Subjects with QT interval greater than 480 milliseconds (msec) or greater than 450 msec if accompanied by a partial bundle branch block, or other clinically significant ECG abnormality at Screening in the judgement of the Investigator.
28. Subjects with diastolic blood pressure less than 50 mmHg or greater than 105 mmHg; sitting heart rate less than 50 beats per minute (bpm) or greater than 110 bpm (after approximately 3 minutes at rest); or heart rate by ECG less than 50 or greater than 110 bpm at Screening.

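### Exclusion 11c exempts melanoma by name and without limit, so known or suspected melanoma does not by itself exclude a subject with new back pain

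*Protocol*

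**What the plan says.** Exclusion 11 opens with "Known history or symptoms suspicious of" and then lists conditions a to i. Item c is "Cancer except cutaneous cancers (e.g., melanoma, squamous cell carcinoma". The wording of item c is the same in the Synopsis and in Section 9.2, so neither place corrects the other. The SAP does not restate the eligibility criteria.

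The rest of the list includes recent spinal fracture, osteoporosis with fracture, "Spinal infection" and cauda equina syndrome. Section 9 gives the overall rule: "Individuals are eligible for this study if they meet all inclusion and no exclusion criteria".

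Four other criteria bear on the same subject:

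- Inclusion 2 requires "Current acute back pain and/or stiffness due to acute and painful muscle spasm starting within 7 days prior to study entry".
- Exclusion 11d names "Constitutional symptoms such as recent unexplained chills or weight loss".
- Exclusion 17 covers inflammatory arthritis or "other diseases known to cause intermittent or chronic pain".
- Exclusion 23 covers any other condition that, in the investigator's opinion, "would adversely affect the subject's ability to complete the study or its measures".

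**The concern.** Most items under exclusion 11 are warning conditions: findings that suggest back pain may have a cause other than simple muscle spasm. In such a list, exempting skin cancers makes sense for those unlikely to spread. Melanoma is a skin cancer that can spread, including to the spine. That is general medical knowledge and does not come from the documents. Giving it as the first example of an exempt cancer therefore works against the item.

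What is at stake is the safety of an individual subject. Someone with known or suspected melanoma and new back pain is not stopped by the one criterion that deals with cancer. If the investigator attributes the pain to spasm, that person can be randomised to 14 days of study drug or placebo, having agreed under Inclusion 4 to stop other pain and spasm medication.

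**Working it through.** The plan states no figure on this point and no arithmetic applies. The check is a reading of 11c against every criterion that could exclude the same subject.

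1. **What 11c exempts.** The parenthesis follows directly on the exempt class and gives examples of it. In its plain reading, melanoma is exempt. Because the stem covers both history and suspicion, the exemption reaches known and suspected melanoma alike.

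2. **Whether the exemption is limited.** It is not. Elsewhere the authors wrote limits where they wanted them: 3 years for spinal fracture (11a), 1 year for spinal surgery (exclusion 5) and 1 year for resolved major trauma (exclusion 6). Item 11c has no limit of time, stage or treatment.

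3. **Whether another criterion closes the gap.**
   - Inclusion 2 excludes a subject whose pain is judged not to come from spasm. That judgement is clinical. Screening (Section 11.2.1) provides history, physical and neurological examination and laboratory tests, and the Schedule of Procedures (Table 2) lists no spinal imaging.
   - Exclusion 11d acts only if constitutional symptoms are present.
   - Exclusions 11g (immunosuppression), 15 (major surgery, among others) and 16 (hospitalisation for major illness in the preceding 3 months) may catch some subjects because of their treatment or course, but not because of melanoma.
   - Exclusion 17 is general and does not name cancer.
   - Exclusion 23 is discretionary and turns on ability to complete the study or its measures, not on the origin of the pain.

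   None of these excludes a subject because of melanoma itself.

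4. **Consequence for the analysis sets.** Enrolling such a subject would not breach 11c. Item 11c would therefore generate no eligibility deviation under SAP Section 7.3.2, and would not remove the subject from the per-protocol population defined in SAP Section 7.2.

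**The case against.** The strongest reply is that 11c does not make anyone eligible; it only withholds one automatic exclusion. Section 9 requires every inclusion criterion to be met, and a subject whose pain is judged malignant fails Inclusion 2 whatever 11c says. This stands. A reader might infer from 11c that a subject with melanoma and back pain is simply eligible, and the documents do not support that. What remains is the narrower case of a subject with melanoma whose pain is attributed to spasm, where an express exemption tells the site that the cancer history is acceptable.

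Second, the scope is unclear. The exemption is for cutaneous cancers, and a site could reasonably hold that disease which has spread is no longer cutaneous and is excluded by 11c itself. The text does not say so, and sites may differ. This is a further reason to reword the item.

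Third, the purpose of 11c is inferred. The protocol never says the item is there to detect malignant back pain. Amendment 1 aims at a healthy, low-risk population, but the exclusion changes it describes concern cardiovascular risk, seizure risk and related or acquainted subjects, so it is no evidence about 11c. The inference rests on the neighbouring items alone, and is reasonable on that basis.

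Fourth, subjects are not left unattended. Acetaminophen rescue is supplied (Sections 7.3.2 and 14), examinations are scheduled on Days 4, 14 and 28, and subjects may withdraw or be withdrawn at any time (Sections 9.3 and 15). This lessens the consequence of a wrong enrolment but does not justify the exemption.

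**Conclusion.** The point holds as a wording error in 11c with a patient-safety consequence of low frequency. Known or suspected melanoma does not by itself exclude a subject with new back pain, and the remaining criteria reduce that gap without closing it. The documents give no rate of melanoma among likely subjects, so no number of affected subjects is offered; it is expected to be small.

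The conclusion rests on three assumptions: that the parenthesis lists examples of what is exempt, that exclusion 11 is meant to remove back pain that is not simple spasm, and that melanoma can spread to the spine.

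A reader might also infer that such subjects would weaken the efficacy result. The documents do not support that as an argument. Even if one such subject in an arm of 80 had no drug effect while the others had the full 0.9 points used in the sample-size section, the mean effect would fall on average by 0.9 × 1/80 = 0.011 points on a 0 to 10 scale. The 0.9 is not assumed for every dose either: the effect sizes in Protocol Table 1 are for the high dose against placebo, and many scenarios give lower doses less or nothing. A non-improving subject who happened to be in the placebo arm would widen the observed difference. No effect on power or on the treatment contrast is claimed.

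**What to change.** In both the Synopsis and Section 9.2, reword 11c so that the exemption expressly covers non-melanoma skin cancers only, for example: *Cancer except non-melanoma cutaneous cancers*.

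Deleting melanoma from the examples would not achieve this. The list is introduced as examples and is not exhaustive, and melanoma would remain a cutaneous cancer, so it would still be exempt. If the sponsor intended a narrower allowance for some history of melanoma, it should state that scope and its limits in the criterion.

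The cost is a few words in two places, with the IRB re-approval that Section 21 requires for an amendment, and a negligible loss of otherwise eligible subjects. The SAP needs no change. SAP Section 7.7.2 refers to a site audit in May 2019, so enrolment may be well advanced. If it is complete, the useful steps are to check the recorded medical histories for melanoma and to carry the corrected wording into later protocols.

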Subjects will return to the clinic to complete the procedures listed in the Schedule of Procedures on Day 4 (± 1 day; Visit 2) and Day 14 (+1 day, End of Treatment [EOT] visit, Visit 3). Subjects must also return to the clinic for a follow-up visit on Day 28 (+3 days, 2-week follow-up visit, Visit 4).

For all subjects, safety laboratory assessments will be performed on Day 1 (Screening/Baseline visit, -3 to 0 days) and Day 14 (Visit 3). In addition, a sample for genotyping will be collected on Day 1 (Screening/Baseline visit). For select sites with additional consenting subjects, pharmacokinetic samples will be collected on Day 4 (Visit 2).

Primary Objective:

- To assess the efficacy of tolperisone daily doses 150, 300, 450, and 600 mg for relief of pain due to acute back muscle spasm.

Secondary Objectives:

- To assess the safety and tolerability of tolperisone in subjects with pain due to acute back spasm.
- To determine the onset of action of tolperisone in treatment of pain due to acute back spasm.
- To determine the duration of pain relief of tolperisone in treatment of pain due to acute back spasm.
- To determine the need for rescue medication when treated with various doses of tolperisone for pain due to acute back spasm.

Endpoints:

Data for primary efficacy analysis will be assessed during the clinic visits by the subject on the study-provisioned tablet provided to each site for use at baseline, and at Days 4 and 14. Additional efficacy endpoints and dosing will be collected daily at specified times from the subjects via a smartphone/trial application for ePROs. At baseline, and at Days 4 and 14, efficacy endpoints will be assessed during the clinic visit on the study-provisioned tablet provided to each site. See the Schedule of Procedures for all assessments to be conducted during the study. For the endpoints below, baseline is defined as the last assessment prior to the first dose of study drug.

Primary Endpoint:

- Subject-rated pain due to acute back spasm using a Numerical Rating Scale (NRS; 0-10 scale, from no pain to worst possible pain) on Day 14 “right now”.

Secondary Endpoints:

Efficacy Endpoints

- Subject-rated pain due to acute back spasm using an NRS (0-10 scale, from no pain to worst possible pain) on Day 4 “right now”.
- Subject rating of medication helpfulness (SRMH; 1-5 scale, from poor to excellent) on Days 4 and 14.

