- Subject-rated NRS (0-10 scale) of pain due to acute back spasm on Days 1 to 14; average over past 12 hours.
- Subject-rated NRS (0-10 scale) of pain due to acute back spasm on Days 1 to 14, average over the past hour.
- Subject-rated NRS (0-10 scale) of average pain due to acute back spasm on rest or movement, rated at the end of the day on Days 1 to 14.
- Time to relief of pain due to acute back spasm using subject-rated NRS (0-10 scale) on Days 1 to 14.
- Clinician’s Global Impression of Severity (CGI-S) (1–5 scale) at baseline (Day 1).
- Clinician’s Global Impression of Change (CGI-C) (1-7 scale from worse to marked improvement) on Days 4 and 14.
- Patient’s Global Impression of Severity (PGI-S) (1-5 scale) at baseline (Day 1).
- Patient’s Global Impression of Change (PGI-C) based on subject’s global assessment

(1-7 scale, from worse to marked improvement) on Days 4 and 14.

- Functionality assessment: fingers to floor distance (FFD) is an index of mobility of the spinal cord and is measured as distance in cm when standing with the spinal cord flexed with complete extension of knee joint, on Days 4 and 14 compared to baseline (Day 1) (assessments should be conducted at the same time of day for all three time points).
- Disability assessment at baseline (Day 1), Day 4, and Day 14: Oswestry Disability Index (ODI) questionnaire (10 questions with one answer each for pain intensity, personal care, lifting, walking, sitting, standing, sleeping, sex life [if applicable], social life, and traveling).
- Use of rescue medications (measured daily, assessed as number of rescue tablets administered by the subject via smartphone/use of trial application). Patients are instructed not to take rescue medications on the day of clinic visits on Day 4 and 14.
- Quality of sleep rated by subjects starting at baseline (Day 1) and on Days 2 to 14.
- Visual Analogue Scale (VAS) score for subject-reported sleepiness measured in the clinic on Day 4.

Safety Endpoints

- Clinical evaluations
 - Vital signs (blood pressure, heart rate, respiratory rate, body temperature)
 - Orthostatic effects on blood pressure
 - Physical examinations
 - 12-lead electrocardiograms (ECGs)
- Laboratory tests (blood chemistry, hematology, urinalysis, and urine pregnancy tests for women of childbearing potential)
- Adverse events (AEs)

Planned Number of Subjects and Sites:

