The primary efficacy endpoint is subject-rated pain “right now” due to acute back spasm using an NRS (0-10) scale, from no pain to worst possible pain for the clinic visit on Day 14. This analysis will be performed using a linear test of trend across doses, using a mixed effect model for repeated measures. The model will include treatment and time as fixed effects, the treatment by time interaction, and the baseline NRS rating as a covariate. Differences in linear trend for each dose level versus placebo will be presented with 95% confidence intervals and associated p-values. The analysis performed for the primary endpoint will be repeated for the NRS at Day 4. Additional analyses for secondary efficacy endpoints will be conducted using repeated measures and analysis of covariance for continuous variables, a Wilcoxon Rank Sum test for categorical variables, and Kaplan-Meier analysis for time to pain relief.

Safety Analysis:

Safety measures will be summarized using descriptive statistics and listed for each subject.

Safety analysis will be based on all subjects randomized who receive at least 1 dose of the study medication. The safety analysis will evaluate AEs and additional safety parameters. The number and percentage of subjects experiencing at least one AE will be summarized by body system, preferred term, and treatment. If appropriate, AEs will also be summarized by intensity and relationship to study drug. Serious adverse events (SAEs), if any, will be tabulated.

Additional safety parameters will be assessed from summaries of physical examinations, 12-lead ECGs and vital signs. The 12-lead ECG results will be categorized as normal, clinically significant abnormal, and not clinically significant abnormal. Hematology, chemistry and urinalysis laboratory test results will be categorized relative to the normal ranges. The changes from baseline for each of these parameters from Screening to EOT will be presented. Complete listings and summary tables for all safety information including AEs, laboratory safety data, ECG, vital signs and physical examination will be included in the study report.

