Use of rescue medications will be summarized using frequency counts and percentages by generic drug name. Average daily use and total use will be tabulated using descriptive statistics. The Shapiro-Wilk test will be used to examine the assumption of normality. If this test is statistically significant (i.e., $p \leq 0.05$) then the assumption of normality is violated and the total rescue medication consumption will be analyzed using a Wilcoxon Rank Sum test. Results will be expressed as median (range) and p-values. However, if the assumption of normality holds (i.e., Shapiro-Wilk p-value > 0.05), then the total rescue medication consumption will be analyzed using an analysis of variance (ANOVA) model with randomized treatment as the main effect. Results will be expressed as means, SDs, and least squares mean difference (LSMD) and SEs with associated 95% CI, and p-values.

All other secondary endpoints will be summarized by dose using descriptive statistics. In addition, the comparison of each group to placebo will be conducted using an ANCOVA model, adjusting for baseline.

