The number of subjects with relief and those censored will be summarized by treatment group for the ITT population. Estimates of the median times will be presented along with their associated 95% confidence intervals. Treatment group comparisons will be summarized with hazard ratios and their associated 95% CI from a Cox Proportional Hazards regression model with treatment as the main effect and p-values from a generalized Wilcoxon test.

The Kaplan Meier plots of time to pain relief by treatment group will be presented and display the subjects with relief and those censored at each study day.

A by subject listing of derived time to relief estimates will also be presented.

7.4.5.9 *Rescue Medication Use*

The use of study provisioned medication will be summarized using frequency counts and percentages for the number of tablets consumed by treatment group for the ITT population. Descriptive statistics will also be presented by treatment group. The number of days of medication use, average daily use (caplets/day of medication use) and total use will be tabulated using descriptive statistics. The frequency and percentage of subjects with rescue medication entry will be presented.

The Shapiro-Wilk test will be used to examine the assumption of normality for total rescue medication use across all dose groups. If this test is statistically significant (i.e., $p \leq 0.05$) then the assumption of normality is violated and the total rescue medication consumption will be analyzed using a Wilcoxon Rank Sum test.

However, if the assumption of normality holds (i.e., Shapiro-Wilk p-value > 0.05), then the total rescue medication consumption will be analyzed using an analysis of variance (ANOVA) model with randomized treatment as the main effect. The LSM and LSMD will be presented with associated 95% CI and p-values comparing each treatment group to placebo.

A data listing of rescue medication use will be presented and include the average number of tablets consumed and total number of tablets rescue medication consumed for each subject.

7.4.5.10 *Oswestry Disability Index*

ODI score (%) will be calculated as $(\text{total score} \times 2) / (\text{number of sections answered} / 10)$, rounded to the nearest integer, where the total score is the sum of the individual section scores.

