Observed ODI score and change from baseline will be summarized descriptively for each treatment group for the ITT population. Each dose group will be compared to placebo using an ANCOVA model with observed value as the response, main effects for treatment group and a covariate adjusted for the baseline ODI score. The LSM, LSMD, 95% CI and p-values will be presented at Day 14.

Individual section scores will be summarized separately for the ITT population by treatment group. The frequency and percentage of subjects in each response category at Baseline, Day 4 and Day 14 will be presented. The comparison of each group to placebo will be conducted using a Wilcoxon Rank Sum test for the Day 14 values and p-values presented.

7.4.5.11 *Visual Analogue Scale of Sleepiness*

The Day 4 VAS ratings of sleepiness will be summarized descriptively by treatment group for the ITT population. Each dose group will be compared to placebo using an ANOVA model with the observed values as the response and main effects for treatment group. The LSM, LSMD, 95% CI and p-values will be presented.

7.4.5.12 *Daily Activities*

Daily activity scores will be summarized categorically for Days 1 to 14 by treatment group for the ITT population. The frequency and percentage of subjects in each response category will be presented. The comparison of each group to placebo will be conducted using a Wilcoxon Rank Sum test for the Day 14 values and p-values presented.

7.4.6 *Statistical/Analytical Issues*

7.4.6.1 *Adjustments for Covariates*

The MMRM model to test for linear trend for the primary endpoint will include a covariate adjustment for the baseline value. Secondary endpoints utilizing an MMRM will be analyzed similarly when a baseline value is captured.

7.4.6.2 *Handling of Dropouts or Missing Data*

Primary and secondary endpoints including all NRS assessments (right now, past 12 hours, past 1 hour, at rest, on movement), Fingers to floor Distance, Clinician's Global Impression, and Oswestry Disability Index assessments will be analyzed using both observed data and data imputed using last observation carried forward (LOCF), if the dropout rate is $\geq 5\%$ (20/400 subjects). In the LOCF method, the most recent non-missing value for the endpoint is carried forward to replace a missing value at a post-baseline visit within a subject. Baseline values will not be carried forward.

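### Total rescue use is compared between arms without adjustment for baseline pain; naming baseline 'right now' NRS as covariate is a free, possibly modest gain in precision (minor, secondary endpoint only)

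*Protocol*

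**What the plan says.** - **Objective and measure.** Among the secondary objectives the protocol lists "To determine the need for rescue medication when treated with various doses of tolperisone for pain due to acute back spasm". The endpoint is recorded daily and is "assessed as number of rescue tablets administered by the subject".
- **Planned tests.** A Shapiro-Wilk test chooses the method. If it is significant, Protocol 17.4.2.2 states that "total rescue medication consumption will be analyzed using a Wilcoxon Rank Sum test", and SAP 7.4.5.9 repeats this. If it is not, "total rescue medication consumption will be analyzed using an analysis of variance (ANOVA) model with randomized treatment as the main effect", and the SAP again agrees. Neither branch has a covariate or a stratum.
- **General statements on adjustment.** The synopsis summarises secondary efficacy methods as repeated measures and "analysis of covariance for continuous variables, a Wilcoxon Rank Sum test for categorical variables". Protocol 17.4.2.2 gives rescue use its own method and then assigns baseline-adjusted ANCOVA to the remaining secondary endpoints. SAP 7.4.6.1 says: "Secondary endpoints utilizing an MMRM will be analyzed similarly when a baseline value is captured".
- **Available covariate.** Baseline 'right now' NRS must be at least 4 for entry (Protocol 9.1, criterion 3). It is taken before dosing on Day 1 (Protocol 11.2.1) and is a covariate in the primary model (Protocol 17.4.2.1, SAP 7.4.4).

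**The concern.** The protocol itself ties rescue use to pain: it is allowed for significant pain (7.3.2) or when pain is severe (section 14). Entry pain, which can run from 4 to 10, is therefore a plausible predictor of how many tablets a subject takes. Entry pain is not balanced by design either, since the SAP stratifies randomisation by site only (6.3.2). If the score is prognostic, leaving it out puts explainable variation into the error term of each comparison of 80 with 80. What is at stake is some power, and some width of the confidence interval, for one secondary objective. The primary analysis is not touched.

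**Working it through.** **1. The plan's own figure.** No power, SD or effect size is stated for rescue use. The only power figures are for the NRS (Protocol Table 1). With 80 per arm, two-sided 5% and a noncentral t on 2×80 − 2 = 158 df, the noncentrality is d × √(80/2). For high dose against placebo this gives 59.5%, 71.0% and 80.8% at d = 0.35, 0.40 and 0.45, against the stated 60%, 71% and 81%. The plan's figures reproduce and are not in dispute.

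**2. Normal branch: ANOVA against ANCOVA.** Let ρ be the within-arm correlation of baseline NRS with total rescue use (assumed). ANCOVA multiplies the variance of the treatment difference by (1 − ρ²), the CI width by √(1 − ρ²), and is worth 80/(1 − ρ²) subjects per arm. Power is shown at an illustrative standardised effect of 0.40, with one df lost for the covariate.

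| ρ | Variance saved | CI width saved | Equivalent n per arm | Power |
|---|---|---|---|---|
| 0 (unadjusted) | 0% | 0% | 80 | 71.0% |
| 0.1 | 1% | 0.5% | 81 | 71.5% |
| 0.2 | 4% | 2.0% | 83 | 72.8% |
| 0.3 | 9% | 4.6% | 88 | 75.0% |
| 0.4 | 16% | 8.3% | 95 | 78.3% |
| 0.5 | 25% | 13.4% | 107 | 82.7% |

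For example, at ρ = 0.3: 1 − 0.09 = 0.91, √0.91 = 0.954, and 80/0.91 = 87.9.

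**3. Non-normal branch: Wilcoxon against a rank test adjusted for baseline NRS.** Two simulations were run with 80 v 80, baseline NRS 4 to 10, and totals capped at 36 tablets. The cap follows from 3 per day on the 14 − 2 = 12 days that are not the Day 4 or Day 14 visit.

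- Simulation A: log-normal/Poisson counts, rate ratio 0.62, 4,000 trials per setting (2,000 under the null), Spearman correlation.
- Simulation B: gamma-Poisson counts with gamma shape 1 and mean 8 at NRS 6.5, rate ratio 0.60, 2,000 trials, product-moment correlation in the placebo arm.

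| Simulation | Correlation | Wilcoxon | Adjusted rank test | Gain (points) |
|---|---|---|---|---|
| A | 0.00 | 67.0% | 66.6% | −0.4 |
| A | 0.18 | 66.7% | 67.5% | 0.8 |
| A | 0.31 | 67.2% | 70.6% | 3.4 |
| A | 0.44 | 68.2% | 76.4% | 8.2 |
| A | 0.56 | 68.0% | 82.9% | 14.9 |
| B | about 0 | 72.9% | 72.9% | 0.0 |
| B | 0.14 | 70.2% | 71.3% | 1.1 |
| B | 0.27 | 68.9% | 71.4% | 2.5 |
| B | 0.39 | 64.3% | 70.3% | 6.0 |

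Read across rows, not down: in B, raising the correlation also adds variance, so the Wilcoxon figure falls. Rejection under the null was 4.4% to 5.5% in A and 4.3% to 5.4% in B.

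**4. Which branch would apply.** In simulation B, Shapiro-Wilk on all five arms together rejected normality in every trial. If rescue counts are skewed in this way, the Wilcoxon branch is the one that will be used.

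**The case against.** Most of the case on the other side stands.

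- **A reader might infer that the plan breaks a promise in its synopsis.** The documents do not support that. The synopsis sentence covers all secondary endpoints in one line and names no covariate for rescue use. Protocol 17.4.2.2 gives rescue its own method and reserves ANCOVA for the other endpoints, and the SAP agrees.
- **A reader might infer that SAP 7.4.6.1 confines adjustment to MMRM endpoints.** It contains no such restriction, and SAP 7.4.5.10 plans an ANCOVA on baseline for the ODI.
- **Rescue use has no pre-dose value of its own.** For VAS sleepiness, SAP 7.7.1 replaces ANCOVA by ANOVA for that very reason, so a treatment-only ANOVA for rescue is consistent. Baseline NRS would be a new covariate, not one promised and dropped.
- **A reader might infer bias from chance imbalance in entry pain.** Randomisation already allows for this in the p-value, and the unadjusted tests keep their type I error.
- **The correlation may be low.** Baseline NRS is a single momentary rating, cut off below 4, set against a capped total over 14 days in an acute condition. PGI-S and ODI are also collected at baseline, so NRS cannot be called the best predictor.

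What remains is narrower. A plausible predictor is already collected, and the primary model already uses it. Neither document gives a reason for leaving it out of the rescue comparison, and adjusting costs essentially nothing if it proves unrelated.

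**Conclusion.** The point holds as a minor suggestion. The planned comparisons are valid but may be less efficient than they could be. It would go too far to say that precision is certainly lost, because the loss exists only if baseline NRS predicts rescue use, and the documents are silent on that.

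Under the assumed counts and rate ratios of about 0.6, the gain in power is nil at zero correlation, about 1 point or less below 0.2, about 3 points near 0.3 and 6 to 8 points near 0.4. The larger gain at 0.56 should not be relied on, given the restricted entry range. In the normal branch the CI would narrow by 4.6% at a correlation of 0.3. All figures take the planned 80 per arm; the exclusion of one site (SAP 7.7.2) may leave fewer.

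**What to change.** Before unblinding, in SAP 7.4.5.9 and Protocol 17.4.2.2:

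1. Name baseline 'right now' NRS as the covariate for total rescue use.
2. In the non-normal branch, which is the likely one, replace the plain Wilcoxon by a rank ANCOVA on baseline NRS, or by a van Elteren test stratified by pre-specified baseline bands (for example 4-5, 6-7 and 8-10).
3. In the normal branch, add baseline NRS to the ANOVA and report the adjusted difference with its 95% CI.
4. If an adjusted estimate with a CI is also wanted in the non-normal branch, take it from a companion count model, such as a negative binomial with treatment and baseline NRS. The rank tests do not supply a difference in tablets.

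The cost is a few sentences, an entry in SAP 7.7.1 and a few lines of code. No new data or subjects are needed.
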